13.4 Analysis Plan

The overall focus of our statistical analysis of the clinical portion of the study will be on the estimation of hazard ratios (HR) and risk ratios (RR) and their two-sided 90% confidence intervals comparing the rituximab and placebo groups on each endpoint of the study. Focusing on estimates and confidence intervals will allow us to assess the range potential efficacies as best we can within the limitations imposed by studying such a rare pediatric population.

Further detail describing the analysis plan will be contained in a Statistical Analysis Plan (SAP) that will be maintained by the SACCC and updated as necessary.

13.4.1 Analysis Populations

Intent-to-Treat (ITT) Sample. All randomized subjects who receive at least a portion of the initial rituximab/placebo infusion will constitute the ITT sample. This sample will be used for evaluation of the primary and secondary clinical endpoints. Subjects will be analyzed in the group to which they were randomized, regardless of compliance with the protocol or withdrawal from the study.

Per-Protocol (PP) Sample. Subjects from the ITT sample who complete the full induction protocol, with complete administration of the prescribed dose at both the initial and subsequent infusions, will make up the PP sample. This sample will capture subjects who both tolerate rituximab well and recover as expected from their transplant.

Safety Sample. All subjects from the ITT sample will constitute the safety sample.

13.4.2 Primary Analysis of Primary Endpoints /Outcomes

We will use competing-risks Cox proportional hazards models to compare treatment groups on the time to endpoint, right-censored at the end of the two-year follow-up period or at time of loss to follow-up. This model, as opposed to a time-to-first-event model, will allow us to estimate a separate hazard function for each type of outcome as well as the overall outcome, and thus assess whether the effect of rituximab is the same for all outcome types¹⁰⁰. Our focus will be on the estimates of these hazard ratios (HR) and their two-sided 90% confidence intervals, with $HR < 1$ indicating rituximab efficacy. We will assess whether HR is constant throughout follow-up, or if the effect of rituximab is confined to early or late portions of the study periods through the use of time-dependent covariates. Model diagnostics will include assessment of the proportional hazards assumption and of each observation for influence on model parameters. The model will be run on both the ITT and PP populations, as events allow.

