Secondary Clinical Endpoints	
Post-transplant outcomes including:
 
 1. Incidence of chronic allograft dysfunction, listing for retransplantation and death during the follow-up period, which will be a minimum of 12 months post-transplant; 2. Incidence of Primary Graft Dysfunction; 3. Incidence of Grade A Acute Rejection during the follow-up period, which will be a minimum of 12 months post-transplant; 4. Incidence of Antibody Mediated Rejection during the follow-up period, which will be a minimum of 12 months post-transplant; 5. Incidence of tacrolimus variability threshold during the follow-up period, which will be a minimum of 12 months post-transplant; 6. Percentage of participants meeting tacrolimus variability threshold who complete tacrolimus variability intervention; 7. Magnitude of change in standard deviation of tacrolimus levels following intervention. 
Post-transplant safety outcomes including:
 
 1. Incidence and severity of infection episodes;

	2. Serious adverse events related to rituximab.
Secondary Mechanistic Endpoints	
 1. Incidence and kinetics of DSA and autoantibodies, specifically Collagen V (CoIV) and k-alpha-1 tubulin ($\kappa\alpha 1T$); 2. Frequency, kinetics, phenotype and function of peripheral B cells; 3. Frequency, kinetics and cytokine profiles of allo- and auto reactive T cells; 4. Incidence and quantity of B cells and B cell proximity to other cells in the graft tissue.
Accrual Objective	50 randomized pediatric lung transplant recipients
Study Duration	
4.5 years (3.5 year accrual + 1-4.5 year follow-up period)
 
All participants will be followed for a minimum of 1 year post-transplant. Participants will continue follow up visits (up to 4.5 years post-transplant) until the last participant completes 1 year of follow-up.

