3.2. Primary Endpoints

The primary endpoint is the earliest time to any of the following events during the follow-up period:

- Chronic Allograft Dysfunction
- Listed for Retransplant
- Death

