8.4. Study Assessments

Subjects enrolled in this study will be followed for a minimum of 12 months post-transplant. Follow up visits will continue as detailed in Appendix 1 until the last participant completes 12 months of follow up (up to 54 months). Subjects may have blood and BAL samples collected at the following timepoints post-transplant:

- Transplant/Randomization-Day 0
- Day: 12
- Weeks: 4-6
- Months: 2, 3, 6, 9, 12, 18 and 24

Clinical safety will be monitored through routine physical examinations and appropriate laboratory assessments. During this period participants will have repeated clinical/laboratory evaluations, as specified in the Schedule of Events (Appendix 1, Schedule of Events- Recipient).

Assessments for the development of adverse events, serious adverse events, infections, rejections, death, PTLD, relisted for transplant or re-transplantation and hospitalizations will be completed at each study visit. All events will be reported using a designated electronic case report form (eCRF).

Chronic allograft dysfunction, relisting for transplant and death data will be collected up to 54 months post-transplant.

Protocol Biopsies

Transbronchial biopsies will be performed routinely as part of standard of care. The histologic evaluations from routine biopsies at day 12, week 4-6, month 3, month 6, month 12, month 18, and at the time of a symptomatic episode will be evaluated by the local pathologist and interpretations recorded on electronic case report forms (eCRFs).

Tacrolimus Standard Deviation Marker

Variability of tacrolimus will be monitored continuously starting 3 months post-transplant, using the calculation of the degree of fluctuation of tacrolimus blood levels over time, described by the standard deviation (SD) of tacrolimus levels.⁸² All outpatient levels obtained at least 3 months post-transplant will be used. In order to ensure the validity of tacrolimus trough levels, clinical sites will agree on quality control measures for obtaining trough levels. A rolling SD will be calculated for every patient using 1-year of tacrolimus levels (at least 3 trough levels). A SD of 2.0 or more (Shemesh et al. manuscript in preparation), an undetectable level or the absence of a tacrolimus trough level for 3 months will trigger a phone call among the site coordinator, the participant, parent(s)/guardian(s) and trained personnel at ISMMS to address barriers to adherence.

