11.1. Participant Completion

All participants will be followed for a minimum of 12 months and up to 54 months after transplantation.

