13.6 Sample Size Considerations

Planning this study indicates a sample-size analysis that is congruent with our focus on estimates and confidence intervals. Accordingly, simulated study data using a Weibull distribution with parameters chosen to match our expectation that the outcome rate in the control group will be 74% at one year and 53% at two years, with hazard ratios of 0.40 and 0.33. For the purposes of the study only large group differences are clinically relevant, and therefore this effect size is reasonable.

Sample-sizes between N = 25 + 25 and N = 30+ 30 are feasible, as argued elsewhere. We also looked at N = 35 + 35, but acknowledge this probably not obtainable.

5000 individual trials were run for each combination of total sample size (N = 50, 60, 70) and true hazard ratio (0.40, 0.33). Each trial's dataset was analyzed using a standard Cox proportional hazards model and the estimated log (HR) and its standard error were obtained. Using the criteria given in **Table 21**, each trial's estimate and upper confidence limit was rated as being "excellent," "good," "fair," or "lacking" in supporting the rituximab efficacy. The obtained proportions are given in **Table 22**.

Table 21: Criteria for Estimating Upper Confidence Limit

Evidence for Efficacy	Estimated Hazard Ratio	Upper 90% Confidence Limit
"Excellent"	<0.55	<0.85
"Good"	<0.60	0.85 – 1.10
"Fair"	<0.70	1.10 – 1.20
"Lacking"	Any	>1.20

Table 22: Upper 90% Confidence Limits by HR and Sample Size

Sample Sizes	25+25		30+30		35+35	
	0.04	0.33	0.04	0.33	0.04	0.33
True Hazard Ratio						
Evidence for Efficacy						
"Excellent"	0.39	0.50	0.46	0.59	0.51	0.64
"Good"	0.22	0.21	0.23	0.21	0.24	0.20
"Fair"	0.07	0.06	0.06	0.05	0.06	0.04
"Lacking"	0.33	0.24	0.25	0.16	0.19	0.12

In addition, although the primary analysis is based on a Cox regression model, a simple power and sample size assessment using the less efficient log-rank test indicates that 25 subjects in each group will provide greater than 80% power to detect a HR of 0.45 for the treatment effect using a one-sided test at the 0.05 level of significance.

14. Identification and Access to Source Data

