7.2. Primary Endpoint

The primary endpoint is a composite of the earliest time from transplant to any of the following events during the follow-up period:

- Chronic allograft dysfunction (defined as the occurrence of confirmed BOS grade 0-p or higher or a diagnosis of Obliterative Bronchiolitis (OB)),
- Listed for re-transplant,
- or Death.

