7.2.2. Primary Analysis of the Primary Endpoint

As the data allow, a Cox proportional hazards model will be used to compare treatment groups on the time to endpoint, allowing for right-censoring at the end of the follow-up period or at time of loss to follow-up. Estimates of the hazard ratios (HR) and their two-sided 90% confidence intervals will be produced. HR estimates <1 will indicate rituximab efficacy. For example, if an HR<0.85 is considered as indicating clear efficacy, then an HR estimate and 90% confidence interval of 0.33 (0.16, 0.68) will provide excellent support for clear efficacy; whereas an HR= 0.55 (0.28, 1.07) would provide fair to good support for efficacy, even though it would fail to reach significance for the usual test of HR= 1.

The model will be run on both the ITT and PP samples, as events allow.

Model diagnostics will include an evaluation of the proportional hazards assumption and of each observation for influence on model parameters. The proportional hazards assumption will be assessed by testing for a significant interaction between treatment group and the time-to-event variable.

An example of SAS code to be used for the primary model:

```
Proc phreg;  
  class treatment_group(ref='Placebo');  
  model event_day * endpoint_status(0) = treatment_group intterm /  
risklimits ties=efron alpha=0.1;  
  intterm= treatment_group_01 * event_day;  
run;
```

Note: *intterm* represents the interaction term that can be used to test the proportional hazards assumption and *treatment_group_01* represents *treatment_group* coded as a 0, 1 variable where 0=placebo and 1=rituximab. This term will be used for testing the assumption only and will not be included in the final model.

To estimate the hazard function of each of the components, separately, the following models will be used.

An example of SAS code to be used for the analysis of competing risks:

*This is the model for Death;

```
Proc phreg;  
  class treatment_group(ref='Placebo');  
  model event_day * endpoint_status(0,1,2) = treatment_group /  
risklimits ties=efron alpha=0.1;  
run;
```

*This is the model for Listed for Re-transplant;

```
Proc phreg;  
  class treatment_group(ref='Placebo');  
  model event_day * endpoint_status(0,1,3) = treatment_group /  
risklimits ties=efron alpha=0.1;  
run;
```

*This is the model for Chronic Allograft Dysfunction;

```
Proc phreg;  
  class treatment_group(ref='Placebo');  

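### The protocol censors the primary analysis at two years, but the endpoint definition, the data collection and the SAP use all 12 to 54 months of follow-up, and nothing reconciles the two

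*Protocol*

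**What the plan says.** The protocol's primary analysis (13.4.2) is "right-censored at the end of the two-year follow-up period or at time of loss to follow-up". The SAP's primary analysis (7.2.2) has no two-year limit: it is a Cox model "allowing for right-censoring at the end of the follow-up period or at time of loss to follow-up".

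The other places that bear on the horizon agree with the SAP:

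- Protocol 3.2: "The primary endpoint is the earliest time to any of the following events during the follow-up period". Section 13.2 repeats this in substance.
- SAP 7.2: "The primary endpoint is a composite of the earliest time from transplant to any of the following events during the follow-up period". SAP 7.2.1 censors subjects without an event at the last time their status is known.
- Protocol synopsis, study duration: "4.5 years (3.5 year accrual + 1-4.5 year follow-up period"; the SAP synopsis gives the same.
- Protocol 11.1: "All participants will be followed for a minimum of 12 months and up to 54 months after transplantation".
- Protocol 8.4: "Chronic allograft dysfunction, relisting for transplant and death data will be collected up to 54 months post-transplant". Appendix 1 has a month 25–54 column in which the endpoint events are assessed.

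The sample-size section (13.6) gives control-arm planning figures at one and two years only and does not state the follow-up used in its simulation.

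**The concern.** Read literally, 13.4.2 treats a subject whose first event comes after month 24 as censored at month 24. The SAP counts the same subject as an event. Both texts describe the primary analysis, and the SAP does not mention the difference.

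Two things are at stake. The first is precision: the trial has 50 subjects and few events, and the cut removes some of them. The second is the estimate itself: if the hazard ratio is not constant over time, the two horizons estimate different averages. A primary hazard ratio should rest on one horizon, fixed before treatment assignments are known.

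**Working it through.** **Inputs.** 25 + 25 subjects (Protocol 3.1, 13.6). Accrual over 3.5 years and follow-up of 1 to 4.5 years (synopsis). Control arm: "our expectation that the outcome rate in the control group will be 74% at one year and 53% at two years". HR 0.40 and 0.33 (text of 13.6; the Table 22 header prints 0.04, taken as 0.40). Assumptions that the documents do not supply: uniform accrual; 74% and 53% read as event-free, because a cumulative event rate cannot fall; loss to follow-up of 0, with 5% and 10% per year as a range; and the course of the hazard after year 2.

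**Planning curve.** Cumulative hazard at 1 year = −ln 0.74 = 0.301; at 2 years = −ln 0.53 = 0.635. Weibull shape = ln(0.635/0.301)/ln 2 = 1.076, so H(t) = 0.301·t^1.076.

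**The plan's own figures first.** Table 22 was re-simulated with 10,000 trials per cell and the Table 21 ratings. Proportion rated Excellent:

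| N per arm, HR | Table 22 | Follow-up 1–4.5 y, cut at 2 y | Full 1–4.5 y |
|---|---|---|---|
| 25, 0.40 | 0.39 | 0.397 | 0.494 |
| 25, 0.33 | 0.50 | 0.501 | 0.633 |
| 30, 0.40 | 0.46 | 0.460 | 0.566 |
| 30, 0.33 | 0.59 | 0.590 | 0.716 |
| 35, 0.40 | 0.51 | 0.516 | 0.630 |
| 35, 0.33 | 0.64 | 0.647 | 0.766 |

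With the cut, all six Excellent cells agree within 0.7 points, and the largest gap in any of the 24 cells is 2.2 points. Following everyone for exactly two years also comes close (largest gap 4.1 points, or 1.6 with 10% yearly loss). Full follow-up without loss is 10–13 points too high. The table therefore fits a horizon of about two years. This is an inference, since 13.6 states neither follow-up nor loss.

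**Expected events at HR 0.40.** Per arm: 25 × the average, over T uniform on (1, 4.5), of 1 − exp{−HR·H(min(T, c))}, with c = 2 for the cut and c = 4.5 for full follow-up.

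- Cut at two years: control 11.0, rituximab 5.2, total 16.3 before rounding.
- Full follow-up: control 14.2, rituximab 7.4, total 21.6.
- Reduction: (21.6 − 16.3)/21.6 ≈ 25%. It is also about 25% at HR 0.33 (20.5 against 15.4), and 22% at HR 1 (28.4 against 22.1).
- Subjects with potential follow-up beyond two years: 2.5/3.5 = 71%.

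**Precision.** SE of log HR = √(1/d_control + 1/d_rituximab).

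- Cut: √(1/11.0 + 1/5.2) = 0.53.
- Full: √(1/14.2 + 1/7.4) = 0.45.
- Ratio, before rounding the SEs: 1.17, so the 90% interval is about 17% wider on the log scale.

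**Sensitivity at HR 0.40.** Same formula, with the hazard after year 2 multiplied by 1, 0.5 or 0.25, or with constant yearly loss:

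| Assumption | Events lost to the cut | 90% interval wider by |
|---|---|---|
| Hazard continues, no loss | 25% | 17% |
| Hazard continues, 5% yearly loss | 23% | 16% |
| Hazard continues, 10% yearly loss | 21% | 14% |
| Hazard halves after year 2, no loss | 15% | 10% |
| Hazard falls to a quarter, no loss | 9% | 5% |
| Hazard falls to a quarter, 10% yearly loss | 7% | 4% |

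**On the plan's rating scale.** In the simulation at 25 + 25 and HR 0.40, moving from the cut to full follow-up raises the chance of Excellent from 0.40 to 0.49 and lowers the chance of Lacking from 0.31 to 0.21. These figures also assume no loss and a continuing hazard.

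**The case against.** The best defence is that the operative plan already has one horizon. Protocol 13.4 leaves further analysis detail to the SAP, and the SAP looks like the later text: 7.3.1 refers to 2016 guidelines, while the latest dated entries in the protocol's reference list are from 2013. SAP 7.2 to 7.2.2 use full follow-up throughout, so the two-year phrase may simply be stale. Much of this stands, and it is why the remedy is mainly a matter of text. But 13.4 does not say that the SAP overrides the protocol. A two-year cut is a stated rule rather than a detail left open, and neither document withdraws it.

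A reader might infer that a two-year horizon has no basis in the design. The documents do not support that. Numbered visits and visit windows end at month 24 (8.6, Appendix 1), as do the listed blood and lavage timepoints (8.4). Routine biopsies are listed only to month 18 (8.4), although histology is the outcome for children who cannot do spirometry (7.5.3). The planning rates also stop at two years. Surveillance is thinner later, so a two-year analysis is defensible. What is missing is a choice between the horizons.

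A reader might also infer that the protocol expects the effect to be early or late. Section 13.4.2 only plans to check whether the hazard ratio is constant, and SAP 7.2.2 tests the same assumption. A difference between the two estimates is possible, but not predicted.

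**Conclusion.** The inconsistency is real and concerns the primary estimate. Protocol 13.4.2 conflicts with the protocol's own endpoint definition, follow-up and data collection, and with SAP 7.2.2.

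Its size is a projection. The 25% loss of events sits near the top of the plausible range, because it needs uniform accrual, no loss and the planning hazard continuing beyond the last planning figure. The textual conflict stands at any value in the range.

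Two stronger inferences should be avoided. The conflict does not show that the trial's evidence rating would change. At an observed HR of 0.40 the upper 90% limit is 0.40·exp(1.645·SE), about 0.84 with full follow-up and 0.96 with the cut. These fall on either side of the 0.85 boundary in Table 21, but the first only just, and it passes 0.85 if the hazard halves after year 2. Nor does the conflict explain the statement in 13.6 of more than 80% log-rank power at HR 0.45: the Schoenfeld formula gives 0.50 with the cut and 0.60 with full follow-up.

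**What to change.** Before unblinding:

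1. Amend Protocol 13.4.2 to censor at the end of each subject's follow-up (12 to 54 months) or at loss to follow-up. This matches the SAP, the endpoint definition and the data collection.
2. Name the result censored at two years as a sensitivity analysis in the SAP.
3. State in 13.6 the follow-up and loss assumed for Table 22, or rerun the table on the chosen horizon. Changing 13.4.2 alone would leave the sample-size basis on what appears to be a two-year horizon.

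The cost is a protocol text amendment and a restated or rerun simulation; no new data are needed. The remaining downside is that events after month 24 come from thinner scheduled surveillance, which the two-year sensitivity analysis would help to show.

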13.4.3 Supportive Analyses of the Primary Endpoints

We will also model the time-to-first-event model within the Kaplan-Meier framework for the primary outcome, as needed, given the likelihood of little to no events for one or more of the 3 outcomes.

Secondary analyses will model each component of the outcome separately with the other components as risk factors, as allowed by the number of events and the sample size.

13.4.4 Analyses of Secondary Endpoints and Safety Outcomes

All secondary endpoint analyses will use the ITT sample and will be assessed during the post-transplant follow-up period, which will be a minimum of 12 months.

Separately for each of the secondary incidence endpoints, we will compare the rituximab and control groups on the proportion of patients in each group with at least one episode of the endpoint by estimating the relative risk of the endpoint with its two-sided 90% confidence interval. The absolute risk difference with 90% confidence interval will also be estimated. These methods assume no, or very low rates of, death and re-transplant in the study period. However, if meaningful numbers of subjects have these outcomes, the risk ratio for each incidence endpoint can be estimated through a Cox proportional hazards model with the incidence endpoint as the outcome and right-censoring at death, re-transplant, or other loss to follow-up, following the modeling process described above for the primary endpoint.

Among subjects who are identified as qualifying for and agreeing to participate in the TVI, we will compare the rituximab and control groups on change in standard deviation of tacrolimus levels following the TVI (described in sections 5.3.3 and 8.4) using an analysis of covariance (ANCOVA) model, in which the standard deviation of tacrolimus levels following intervention is the outcome, and study group and pre-intervention standard deviation of tacrolimus levels are the predictors. The group effect with its 90% confidence interval will be estimated.

For safety outcomes, we will analyze each type of infection separately (bacterial, fungal, or viral, including RVI, CMV, and EBV), as well as for all types of infections combined. We will first determine the incidence of bacterial, fungal and viral infections in the rituximab and control groups. 'Incidence rate' will be the number of infections per patient-month, and we will focus on the estimates and associated 90% confidence intervals for the ratio of such rates (RR), where $RR > 1.0$ indicates greater infection rates for rituximab. Of course, infection events are biologically related within patient, thus, relative to perfect independence of events, greater proportions of patients will experience more episodes of the same type of infection and greater proportions of patients will experience no episodes. Accordingly, a Poisson regression models offset for months of follow-up and adjusted for overdispersion will be used to compare groups on the rate of each type of infection and any infection.

Serious adverse events related to rituximab will be reported by their incidence rate per patient and per infusion with 90% confidence intervals. Adverse events will be summarized by treatment group, with 90% confidence intervals.

